## 2.5 Exploratory efficacy analyses

An alternative definition of the secondary endpoint of symptom resolution will be considered in an exploratory analysis. We will evaluate time to sustained symptom resolution, defined as time from randomization until the first day in which no symptoms are reported and are not reported for the duration of the study. The analysis of time to sustained symptom resolution will follow the methods described for the secondary endpoint evaluation symptom resolution in the previous section. Time to symptom resolution based on symptom subsets (i.e. respiratory, systemic) will be similarly analyzed, additionally excluding participants who did not report symptoms from the specified subset at screening.

Time to disease progression will be defined as the time from randomization until the first day of a two point or more increase in either cough or shortness of breath persisting for at least 48 hours or an increase to a score of 4 or 5, or first day of admission to the emergency department, hospitalization, or death. Analysis and reporting of results will be done following methods detailed for time to symptom resolution.

Freedom from SARS-CoV-2 infection by oropharyngeal and nasal swabs at Day 5, 7, 10, and 14 will be modeled using a multivariable logistic regression model adjusted for age and sex. The odds ratio will be presented along with its 95% confidence interval.

Similar approaches to those used for evaluating SARS-CoV-2 viral load in oropharyngeal tests over time and AUC will be used to evaluate viral load in nasal tests.

Correlation between virology and symptomology will be characterized by evaluating the relationship between CT values obtained from the oropharyngeal tests and each symptom through two main approaches. For symptoms graded on an ordinal scale, we will calculate a Spearman correlation and assess significance with a Z-test. For variables that capture presence of a symptom, differences in the median CT values by presence or absence of the symptom will be presented and assessed via a Wilcoxon rank sum test.

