9 SUBJECT MANAGEMENT

9.1 Subject Follow-up

9.1.1. In home assessments.

Participants will complete an at-home symptom questionnaire by REDcap on each day of follow-up through day 28, including in-home assessments of temperature and O2 saturation. These assessments will be reviewed daily by a clinical research coordinator, and patients will be telephoned by a physician if they report an elevated temperature, diminished O2 sat (<94%), or signs/symptoms of respiratory or cardiopulmonary distress (e.g. shortness of breath, dyspnea on exertion). On each day through day 28, patients will also be instructed to collect an anterior nare swab in a pre-labeled container and to store these specimens in a refrigerator at 2°C to 8°C, and to bring these in to their next scheduled appointment. Prior to the optional follow up visits at months 4, 7 and 10, participants will complete an at-home symptom questionnaire and will be asked to collect a stool specimen to bring to their next scheduled appointment.

9.1.2. Follow-up in-clinic assessments.

[figure not shown]
Participants will be seen at follow-up visits at Day 1±1, 3±1, 5±1, 7±1, 10±1, 14±1, 21±1, and 28±1. At each visit, a subjective medical history will be performed, including assessments for use of any concomitant medications. Vital signs will be obtained (temperature, blood pressure, pulse rate per minute, breath rate per minute and oxygen saturation), and oropharyngeal and anterior nare swabs will be collected. Participants will also submit at-home collected anterior nare swab specimens for evaluation. Clinical laboratory measurements will be performed at days 5±1 and 14±1 to assess for safety, with additional clinical laboratory assessments performed as needed for clinical follow-up and/or patient management. Additionally, ~25 mL peripheral blood will be collected from study participants at enrollment and at Days 5±1, 14±1, and 28±1 for processing and cryopreservation into a specimen biobank. Safety and tolerability of Lambda will be assessed by adverse event (AE) monitoring, vital signs assessment and clinical laboratory tests. Patients will reach the end of study at day 28±1 of follow-up. Optional long-term follow up visits will be scheduled 4, 7, and 10 months post-enrollment. The window of ±3 weeks is allowed for these long term follow up visits.

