9.3 Virologic assessments

Oropharyngeal and anterior nare swabs for SARS-CoV2 RNA will be collected using a standardized technique at all study visits. Additionally, participants will be instructed in collection of anterior nasal swabs at home and asked to collect a swab each day. We will ask participants to collect stool at home (between days 0-3, 10-14, and 21-28; and at 4, 7 and 10 months post-randomization). All swabs will be collected in viral transport media or phosphate buffered saline. Stool will be collected in stabilization tubes, kept at room temperature, and brought to the next study visit. Samples collected in the clinic will be refrigerated and transported the same day to the Stanford clinical virology laboratory for processing. We will ask that swabs collected at home be stored in a 4 degree refrigerator until their study visit, at which point they will be transferred to the study team and transported to the clinical virology laboratory. Fridges will be provided to the participants at enrolment. In the clinical virology laboratory, samples will undergo automated nucleic acid extraction followed by a FDA-cleared quantitative real-time PCR assay for SARS-CoV-2, which will generate both qualitative (positive or negative) and quantitative (estimated viral copies) results. The assay is validated for nasopharyngeal, oropharyngeal, and anterior nare samples. The stool assays have been analytically validated and are undergoing clinical validation.

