Area under the curve (AUC) will be defined by a single participant's logarithmic base 10 viral load from oropharyngeal tests collected on days 0, 1, 3, 5, 7, 10, and 14. AUC will be calculated by the trapezoidal rule, using exact times of collection of each OP swab. Multiple imputation using chained equations will be used to impute missing viral load data prior to AUC calculation. Five data sets will be imputed, and imputed values will be calculated using non-missing viral load on each of the 7 sample collection days, treatment arm, age, sex, and whether or not a participant was hospitalized. A pooled linear regression model will be fit to log-transformed AUC as a function of treatment, age, and sex using the 5 imputed data sets. Difference in AUC by treatment arm and corresponding 95% confidence intervals will be reported using Rubin's Rules. The difference in AUC by treatment arm will also be done after refitting the model without participants who were hospitalized to assess sensitivity of results.

The incidence of hospitalizations and emergency department visits will be estimated for each arm, with 95% confidence intervals.

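### SAP 2.5 sets no unit of analysis for the Ct–symptom tests; if swabs are pooled over visits, as the wording suggests, within-participant correlation is ignored and p-values will tend to be too small

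*SAP*

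**What the plan says.** The last paragraph of SAP section 2.5 sets out to characterise how virology and symptoms go together by "evaluating the relationship between CT values obtained from the oropharyngeal tests and each symptom through two main approaches". The first approach is for graded symptoms: "For symptoms graded on an ordinal scale, we will calculate a Spearman correlation and assess significance with a Z-test". The second is for yes/no symptoms: "differences in the median CT values by presence or absence of the symptom will be presented and assessed via a Wilcoxon rank sum test". The paragraph does not say which visits supply the Ct values, whether a participant contributes one value or many, or how repeated values are handled. SAP section 2.2 sets alpha at 0.05 by default.

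The data are repeated. Protocol section 9.1: "Participants will be seen at follow-up visits at Day 1±1, 3±1, 5±1, 7±1, 10±1, 14±1, 21±1, and 28±1". Protocol section 9.3: "Oropharyngeal and anterior nare swabs for SARS-CoV2 RNA will be collected using a standardized technique at all study visits". SAP section 2.4 shows that Day 0 is sampled too, since its AUC uses "oropharyngeal tests collected on days 0, 1, 3, 5, 7, 10, and 14". Protocol section 9.1.1 has participants record symptoms every day through Day 28, so a symptom score can be paired with each swab.

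The protocol does not describe this analysis, and it is not in the SAP's list of exploratory endpoints.

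**The concern.** The Spearman Z-test and the Wilcoxon rank-sum test count every Ct–symptom pair as new information. Repeated pairs from one person are not new to that degree. If a participant tends to run a high or low Ct and also tends to report more or fewer symptoms, the pooled tests overstate the effective sample size, and the p-values come out too small.

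Pooling is the natural reading because the SAP names its swabs when it means particular ones. Section 2.4 lists the AUC days, section 2.7 refers to the baseline swab, and the same section 2.5 fixes the days for "Freedom from SARS-CoV-2 infection by oropharyngeal and nasal swabs at Day 5, 7, 10, and 14". Only the Ct–symptom analysis refers to the oropharyngeal tests without limit. Section 2.4 also puts a participant random effect in its model of viral load from oropharyngeal tests, so the SAP recognises the correlation there but not here.

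Pooling also changes what the coefficient means. Protocol section 2.1.1 cites a report in which viral load fell after diagnosis as symptoms resolved. If Ct rises and symptoms fade over the same weeks, pooled data will show a correlation even when, on any given day, the participants with lower Ct are no more symptomatic than the others.

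At stake are the p-values and interpretation of a descriptive analysis that could be read as evidence that viral load and symptoms track each other.

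**Working it through.** The documents give no power, p-value or within-person correlation for this analysis, so there is no figure to reproduce. The ICCs below are assumptions, shown as a range.

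**Inputs from the documents**
- 120 participants (SAP 1.1).
- m = 8 follow-up swabs per participant (Protocol 9.1 and 9.3), or 9 with Day 0 (SAP 2.4).
- Alpha 0.05 (SAP 2.2), taken as two-sided.
- Pooled pairs: 120 × 8 = 960.

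**Formula.** With no true association and exchangeable correlation within participants, the variance of a pooled correlation is inflated by about

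DE = 1 + (m − 1) × ICC_Ct × ICC_symptom

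and the actual type I error is 2 × [1 − Φ(1.96 / √DE)].

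Example at ICCs 0.5 and 0.5: DE = 1 + 7 × 0.25 = 2.75, and 1.96 / √2.75 = 1.18, so the error is 0.237. The effective number of pairs is 960 / 2.75 = 349.

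**Simulation of the named tests.** 120 participants, m = 8, no true association, 1,500 runs per row. The symptom was cut to five ordered levels for Spearman with a Fisher Z-test, and to present/absent for the Wilcoxon test. The Monte Carlo standard error is about 0.006 near 0.05.

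| ICC Ct / symptom | DE | Formula | Spearman Z | Wilcoxon |
|---|---|---|---|---|
| 0 / 0.5 | 1.00 | 0.050 | 0.045 | 0.048 |
| 0.2 / 0.2 | 1.28 | 0.083 | 0.089 | 0.076 |
| 0.3 / 0.3 | 1.63 | 0.125 | 0.109 | 0.091 |
| 0.5 / 0.3 | 2.05 | 0.171 | 0.153 | 0.138 |
| 0.5 / 0.5 | 2.75 | 0.237 | 0.195 | 0.179 |
| 0.7 / 0.7 | 4.43 | 0.352 | 0.318 | 0.283 |

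From 0.3/0.3 upward the simulated values lie below the formula. A likely reason is that cutting the symptom into categories lowers its correlation within a person. The simulated columns are the better guide to the tests in the SAP.

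**With Day 0 (m = 9), ICCs 0.5/0.5:** DE = 1 + 8 × 0.25 = 3.00 and the formula gives 0.258. Simulation (1,000 runs) gave 0.212 for Spearman and 0.173 for Wilcoxon.

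**One observation per participant (same m = 8 settings, Spearman):** 0.042 to 0.054 for a single visit and 0.049 to 0.062 for participant means. The inflation comes from pooling and disappears without it.

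**Shared time course.** Ct and the underlying symptom scale were given opposite time trends of 0.5 per standard deviation of visit number (an assumed slope), with unit variance around the trend and ICCs 0.3/0.3. There was no association at any single visit. The trend alone implies a pooled correlation on the underlying scale of −(0.5 × 0.5) / (1 + 0.5²) = −0.25 / 1.25 = −0.20. With 960 pairs, both pooled tests rejected in all 300 runs. The single-visit Spearman test rejected in 3%.

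**The case against.** The strongest reply is that the SAP never says the swabs are pooled. Its words also fit a visit-by-visit analysis or one value per participant, and on either reading the tests hold their level. This stands. A reader might infer that the p-values are certainly too small, but the documents do not support that. What they show is an unstated unit of analysis, with pooling the more natural reading. Visit-by-visit testing would have its own cost, because it multiplies the tests across symptoms and visits.

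The size of the inflation is assumed. This also stands: no ICC is given, and if either is zero there is no inflation. A reader might reach a larger figure by taking a symptom as constant within a person. At a Ct ICC of 0.3 the formula then gives DE = 1 + 7 × 0.3 × 1 = 3.1 and an error near 27%. That does not fit symptoms that resolve during follow-up.

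The time trend is a separate matter from clustering. It produces a real association over follow-up, not a chance one, and the SAP does not claim to estimate a same-day link. This is right as far as it goes. The trend changes what is estimated, so the SAP needs to say which association it wants. Nor can one assume that nearly everyone follows the trend, since asymptomatic people are eligible.

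A reader might also infer that this analysis underpins shedding as a meaningful endpoint. The documents do not say so. Their rationale for shedding is transmission (Protocol 2.1.1), and section 2.1.1 notes that sputum and stool shedding often outlasts symptoms.

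**Conclusion.** The point holds in conditional form. SAP 2.5 names two tests that assume independence, applies them to repeatedly sampled Ct values, and gives neither a unit of analysis nor an adjustment. If swabs are pooled over visits, a nominal 5% test has a simulated type I error of about 8% to 20%. That rests on eight swabs from each of 120 participants, exchangeable correlation, and assumed ICCs of 0.2 to 0.5 for both measures. A shared time course is a further reason not to read a pooled correlation as a same-day association.

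The consequence is minor. The analysis is exploratory, does not compare arms, and feeds no primary, secondary or stopping decision.

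**What to change.** State in SAP 2.5 which swabs enter, how each is paired with a symptom record, and whether the target is a same-day association or an association over the whole of follow-up.

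For a same-day association, keep the rank methods. Compute the Spearman coefficient or the rank-sum comparison within each visit day, combine them over days into one estimate per symptom, and obtain confidence intervals and p-values by resampling or permuting whole participants. This respects the repeated swabs, removes the common time trend and avoids a separate test at every visit.

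An alternative is a model for Ct with a participant random intercept and study day as a covariate. It must allow for Ct values beyond the detection limit: SAP 2.4 substitutes 42 for these, and an ordinary linear model would handle a pile-up at that value poorly. This is a reason to prefer the rank approach.

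The cost is a few sentences in the SAP and a little more programming, with no new data and no change to the design. The p-values will probably be less favourable than those from pooled tests.

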## 2.6 Safety analyses

The frequency of adverse events and serious adverse events will be tabulated by type and by treatment arm. AEs will be compared by arm using the Chi-squared test or Fisher's exact test, as appropriate, in the safety analysis set.

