	Phase 2 studies established the optimal dose for virologic suppression and minimizing treatment-related adverse events for hepatitis C at 180 mcg; this dose is also currently being used in hepatitis D trials.
Screening, enrolment, randomization, and follow-up of participants	Patients will be screened, and a baseline physical examination and laboratory assessment performed. Eligible patients will be randomized 1:1 to receive Lambda 180 mcg SC (intervention arm) or normal saline placebo (control arm) (Day 0). Patients will complete an at-home symptom questionnaire on each day of follow-up, including in-home assessments of temperature and O ₂ saturation and collection of anterior nare swabs and stool. Patients will then be seen at follow-up visits at Day 1±1, 3±1, 5±1, 7±1, 10±1, 14±1, 21±1, and 28±1. At each visit, vital signs (temperature, blood pressure, pulse rate per minute, breath rate per minute and oxygen saturation), will be performed. Efficacy of Lambda will be assessed by analysis of COVID-19 in respiratory secretions obtained by oropharyngeal swabs collected consecutively at each visit, and by anterior nare swabs collected daily at home. Clinical laboratory measurements (CBC, chemistries, LFTs) will be performed at enrollment and Days 5±1, and 14±1. Additionally, ~25 mL peripheral blood will be collected from study participants at enrollment and at Days 5±1, 14±1, and 28±1 for processing and cryopreservation into a specimen biobank. Safety and tolerability of Lambda will be assessed by adverse event (AE) monitoring, vital signs assessment and clinical laboratory tests. Patients will reach the end of study at day 28±1 of follow-up.
Primary Outcome	Duration of viral shedding of SARS-CoV-2 virus
Safety monitoring	Frequency of adverse events and serious adverse events will be analyzed in all study participants.
Planned interim analysis	An interim analysis will be performed and analyzed by a data and safety and monitoring board after 50% of study participants are enrolled and have completed 1 day of follow-up following study drug administration.

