2.2. SAFETY AND TOLERABILITY OF LAMBDA

Approximately 3,743 subjects (including 237 healthy subjects; 3,276 subjects with HCV; 197 subjects with HBV; and 50 subjects with HDV) have received Lambda to date.

In a study of healthy volunteers administered a single s.c dose of lambda up to 7.5ug/kg, reversible dose-related increases in liver transaminases (ALT and AST) were seen in 5/17 (29.4%) subjects. One of the 2 subjects treated with Lambda 7.5 μ g/kg experienced reversible Grade 3 elevation of ALT. Transaminase elevations were not associated with increases in bilirubin. Mild dose-proportional decreases in serum fibrinogen were reported for 7 subjects.

In a second healthy volunteer study, the most common AEs associated with s.c administration of lambda were abdominal pain and venous puncture site hematoma. All AEs were mild in intensity. One (3.3%) subject in the 180- μ g group had reversible Grade 1 elevations of AST and ALT not associated with clinical symptoms or bilirubin elevations.

In a recently completed 48-week study of patients with chronic hepatitis delta virus infection, treatment with 180ug lambda, 7/14 (50.0%) patients reported a Grade 3 or 4 treatment-related AE with the following frequencies: injection site reaction 1 (7.1%), ALT or AST increase 5 (35.7%), bilirubin increase 2 (14.3%), decreased neutrophil count 1 (7.1%), flu-like symptoms including fever/chills 9 (64.3%), arthralgia or myalgia 7 (50.0%) and fatigue 8 (57.1%). At the end-of-treatment ALT or AST $>5\times$ ULN $<10\times$ ULN was reported in a single patient. There were no increases in bilirubin $>2\times$ ULN concurrent with increases in ALT or AST at the end-of-treatment. In other studies of lambda as a combination therapy for hepatitis B or C, clinically meaningful increases in total bilirubin occurred in 7.6% and 2.6% of patients dosed with Lambda/Ribavirin (RBV) and Lambda/RBV/Daclatasvir (DCV), respectively. Similarly, increases in serum ALT were noted in 6.2% and 3.7% of subjects on Lambda/RBV and Lambda/RBV/DCV, respectively. All increases were manageable with dose withholding, reduction, or discontinuation.

Lymphopenia was not seen with any significance in prior Lambda studies of 48 weeks. Pyrexia occurred at a frequency of 9.9% of patients treated with the 180ug lambda + RBV.

IFN-based treatment induces a variety of psychiatric adverse effects, including depression, manic condition, acute and chronic cognitive dysfunction, suicidal behavior, and relapse of

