5.3. Safety evaluations

- Frequency of adverse events and serious adverse events by standardized DAIDS AE grading criteria (see appendix)

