## 1.4 Safety endpoints

Safety endpoints include all adverse events by standardized DIADS AE grading criteria, vital signs, and clinical laboratory tests from time of randomization until the patient completes their study participation.

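### SAP 1.4 names vital signs and laboratory tests as safety endpoints, but only adverse-event counts are analysed, so ALT, AST and bilirubin are not compared between arms on their own scale

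*SAP*

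**What the plan says.** **Endpoints.** Besides graded adverse events, SAP 1.4 (Safety endpoints) lists "vital signs, and clinical laboratory tests from time of randomization until the patient completes their study participation". Protocol 9.1 takes the same view: "Safety and tolerability of Lambda will be assessed by adverse event (AE) monitoring, vital signs assessment and clinical laboratory tests". Protocol 5.3 is narrower and lists only the frequency of adverse events and SAEs under DAIDS grading.

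**Measurements.** The Protocol synopsis states: "Clinical laboratory measurements (CBC, chemistries, LFTs) will be performed at enrollment and Days 5±1, and 14±1". Protocol 9.1 gives the purpose: "Clinical laboratory measurements will be performed at days 5±1 and 14±1 to assess for safety". Vital signs are taken at every visit.

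**Analysis.** SAP 2.6 says "The frequency of adverse events and serious adverse events will be tabulated by type and by treatment arm" and then "AEs will be compared by arm using the Chi-squared test or Fisher's exact test, as appropriate, in the safety analysis set". Protocol 12.5 says the same. Neither mentions a laboratory value, a vital sign or a tabulation by grade.

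**Known liver effects.** Protocol 2.2 reports, for healthy volunteers given single doses up to 7.5 µg/kg, that "reversible dose-related increases in liver transaminases (ALT and AST) were seen in 5/17 (29.4%) subjects". In a second healthy-volunteer study, one subject (3.3%) in the 180 mcg group had reversible Grade 1 AST and ALT rises without a rise in bilirubin. ALT or AST increases are listed for 5/14 (35.7%) in a 48-week hepatitis D study. In combination-therapy studies, ALT rises occurred in 6.2% and 3.7% and bilirubin rises in 7.6% and 2.6%.

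**The concern.** Safety compared with placebo is a secondary objective (Protocol 3.2). Followed as written, the SAP gives two of its three declared safety endpoints no analysis of their own. The liver tests are where this matters most. They are the laboratory effect the Protocol documents best, they are measured before dosing and twice after, and a paired baseline is available for each participant. A count of events by type turns each series of values into yes or no and counts a Grade 1 and a Grade 4 rise alike. A shift in ALT that mostly stays below 1.25 x ULN, where DAIDS Grade 1 begins, would hardly appear in such a table. If the laboratory summaries are chosen only after unblinding, there is also no pre-specified choice of analyte, day or scale to hold the report to.

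**Working it through.** **Is there another analysis of these endpoints?** The documents state no power or event figure for safety, so there is none to reproduce. The first check is textual.

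- SAP 2.2 and Protocol 12.2 promise descriptive statistics for key patient variables and plots over time, but name no post-dose laboratory values or vital signs.
- SAP 2.7 uses ALT only as one item in a baseline risk-factor count.
- SAP 5 and Protocol 11.2 give the monitoring board 24-hour safety data, plus Day 5 blood counts in about 25% of patients. This is not an arm comparison of liver tests.
- Protocol 10.1.2 grades laboratory results on the DAIDS scale and captures events of every severity. ALT and AST rises therefore do reach SAP 2.6, as events.

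So the values are compared as counts of graded events and in no other way.

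**What the planned count can detect.** Inputs: 60 per arm (SAP 1.1) and alpha 0.05 (SAP 2.2), taken as two-sided. With k events against none, the two-sided Fisher p-value is 2 x C(60,k)/C(120,k):

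- k=5: 2 x 5,461,512/190,578,024 = 0.057
- k=6: 2 x 50,063,860/3,652,745,460 = 0.027

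At least 6/60 (10%) against 0/60 is therefore needed. Exact power, by summing binomial probabilities over all tables with p at or below 0.05 (the placebo rates are assumptions):

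| Lambda rate | Placebo 0% | 1% | 2% | 5% |
|---|---|---|---|---|
| 6.2% | 17% | 10% | 6% | 2% |
| 10% | 56% | 40% | 28% | 9% |
| 29.4% | >99% | >99% | 99% | 94% |

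**What a comparison of the values would add.** The documents give no ALT distribution, so these inputs are assumptions: log ALT with SD 0.6 and median 0.65 x ULN, baseline to follow-up correlation r, one follow-up value, 60 per arm. The model is

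follow-up = ln 0.65 + r(baseline - ln 0.65) + 0.6 x sqrt(1 - r²) x e + effect,

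with e standard normal. An event is a DAIDS grade higher than the participant's own baseline grade (cut-points 1.25, 2.5, 5 and 10 x ULN). Fisher on events is set against a linear model of log ALT on arm and baseline.

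*Every Lambda patient's ALT rises 1.3-fold, r from 0.5 to 0.8.* Events occur in about 6-9% on placebo and 17-19% on Lambda. Power is 26-33% for Fisher and 79-98% for the adjusted model.

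*Only some Lambda patients respond, r=0.7* (4,000 simulated trials per row):

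| Responders | Rise | Fisher | Adjusted model |
|---|---|---|---|
| 10% | 3-fold | 14% | 23% |
| 10% | 5-fold | 22% | 35% |
| 20% | 3-fold | 47% | 61% |
| 20% | 5-fold | 67% | 81% |
| 30% | 3-fold | 77% | 90% |
| 30% | 5-fold | 94% | 98% |

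Across repeat runs the gain is about 9-17 points, except in the last row, where both tests are near their ceiling and it is about 4.

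**The case against.** **The liver signal is compared between arms.** This stands. A reader might infer that liver tests are never compared. The documents do not support that, because graded rises are adverse events under Protocol 10.1.2 and are tested in SAP 2.6. What is missing is a comparison of the values and of their severity.

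**The count already respects baseline.** This also stands. The laboratory exclusions in Protocol 6.3 set no ALT, AST or bilirubin limit and admit platelet counts already in a DAIDS grade, so a reader might infer that abnormal starting values would be counted as events. But Protocol 10.1.1 defines an adverse event as a deviation from baseline health, including worsening of existing conditions. A stable abnormal value is not an event. Nor does SAP 2.7 show that participants with baseline ALT of 94 or more are expected; it only lists that level as a risk factor.

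**The evidence at this dose is milder.** This stands in part. The 5/17 comes from doses up to 7.5 µg/kg, which is 525 mcg at an assumed 70 kg. At 180 mcg Protocol 2.2 reports 3.3%, Grade 1. The hepatitis figures come from longer or combined treatment. But 3.3% comes from a single subject, and liver tests are still drawn here for safety.

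**Protocol 5.3 lists only adverse-event frequency.** True, and it matches the planned analysis. But SAP 1.4 goes further, so the documents differ and SAP 2.6 does not deliver what SAP 1.4 declares.

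**The power gain depends on the pattern of effect.** This stands. A uniform shift favours the adjusted model most, while Protocol 2.2 describes rises in a minority of subjects.

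**Conclusion.** The gap is real and does not rest on any simulation: laboratory tests and vital signs are declared safety endpoints, and nothing in either document plans to summarise or compare their post-dose values. It has no bearing on the primary efficacy conclusion, but it leaves a stated secondary objective partly unaddressed and should be corrected.

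Its size is moderate. A liver signal near the 29.4% healthy-volunteer rate would be found by the planned test. One near 6% would usually be missed. The adjusted comparison had more power in every setting tried, but the gain runs from a few points to more than 50, depending on assumptions that the documents cannot settle (ALT spread, correlation, and whether all patients or only some respond). A reader might infer that the plan discards most of the liver information; the responder scenarios show that this is not established.

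**What to change.** In SAP 2.6 and Protocol 12.5 add:

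1. For ALT, AST and total bilirubin, the arm difference with 95% CI at Day 5 and at Day 14, from a linear model on the log value adjusted for the participant's baseline value, age and sex. Report it as a ratio and label it supportive and unadjusted for multiplicity.
2. For the key laboratory tests, a shift table by arm from baseline DAIDS grade to worst post-dose grade, so that severity is visible as well as occurrence.
3. For the other laboratory tests and vital signs, change from baseline summarised by visit and arm.

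Run these in the safety population of Protocol 12.1, and bring Protocol 5.3 and SAP 1.4 into line on what the safety endpoints are.

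The cost is SAP and Protocol wording and a few tables. All the data are already collected, and no procedure or sample size changes. The downside is several more descriptive comparisons without multiplicity control: three analytes on two days make six.
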